15.3 Data management

Data will be entered into the REDCap database and maintained at WCM by trained Radiation Oncology data managers.

The system provides audit trails that track creation and modification of records that include user ID and timestamp. Once entered, the data is subjected to validation procedures that are executed either immediately or upon saving the eCRF page or during the batch validation process. Validation failures that are identified before the page is saved can be corrected immediately. Validation failures during saving of the eCRF page and during batch validation processes will generate a discrepancy. Depending on the database account privileges, the data managers may be able to correct a discrepancy or if not, route it to the project data manager at WCM who can take appropriate action to correct the problem. Data clarification forms can also be printed out when necessary to be sent to the project data manager. Once the discrepancy is closed, by marking "resolved" or "irresolvable", the data is marked clean and an audit trail is generated by the system.

All key end points will be source verified by a second person and errors will be corrected. Once the data is verified and all discrepancies are closed, the data can be locked/frozen. Locking

and freezing can be done at different granular levels and will follow institutional SOPs and any specific requirements for the project.

Security measures that will be taken in order to protect patient data will include firewall technology and database level security which will be achieved by assigning roles and privileges to different levels of users and by requiring that the users authenticate themselves using user ID and password. Additional security for data transfer between remote clients and servers will be achieved by using digital certificates/SSL. All data will be backed-up to tape periodically according to the Institutional SOPs. All data will be stored for at least 5 years following the termination of this study.

15.4 Confidentiality

The medical, hospital and research records associated with this study are considered confidential. Members of the treating team and designated study assistants will have access to the records as required to administer treatment and comply with the protocol. Neither the name nor any other identifying information for an individual will be used for reporting or publication regarding this study. All laboratory and baseline data will be de-identified and transferred via secure links to the Study Biostatisticians. Patient records will be made available for inspection to auditing agencies to satisfy regulatory requirements.

16.0 Statistical Considerations

This trial is designed to test the feasibility of the combined regimen, defined as limitation of the acute effects to < 10% Grade 3 events.

16.1 Endpoints

16.1.1 Primary endpoint

The primary endpoint for the study is acute toxicity occurring within 60 days after treatment; the proportion of patients with grade II or III acute skin toxicity.

16.1.2 Secondary endpoints

Acute toxicities, Quality of Life of patients before during and after treatment
Late toxicity 60 days post treatment including brachial plexopathy, fibrosis and telangiectasia; the proportion of patients with grades 2 or higher toxicity

16.1.3 Exploratory endpoints

Local recurrence
Distant recurrence/metastases
Survival

16.2 Analysis Populations

All registered patients will be included in these analyses (intent to treat).

Statistical Considerations Sample Size and Interim Analysis Plans

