4.2 Measuring The Late Toxicities Of Breast Radiation

Radiation-induced breast fibrosis is another important late effect of radiotherapy with a commonly reported incidence of 5-15% [17-18]. Manifestations of radiation-induced breast fibrosis include pain, cosmetic deformities, and diminished quality of life. Clinically, radiation-induced breast fibrosis is characterized by skin retraction, atrophy, toughness to palpation, and decreased tissue compliance with associated functional limitations. Visual assessment and palpation are the most important clinical investigations of the skin in radiotherapy but they

are subjective and unquantitative.

Hoeller et al. recently reported a careful comparison of The Radiation Therapy Oncology Group (RTOG) and Late Effects Normal Tissue Task Force subjective, objective, management, and analytic (LENT/SOMA) scores for late breast toxicity after radiation in a group of breast cancer patients. [19] In comparison, when LENT/SOMA criteria were used, telangiectasia and pigmentation were upgraded in 34% and 36%, respectively, and telangiectasia was downgraded in 45%. Inter-observer variability was similar for both classification systems and ranged from Cohen's kappa 0.3 (retraction) to 0.91 (telangiectasia). The authors concluded that LENT/SOMA criteria seem to be the better in grading and recording late radiation toxicity compared with the RTOG scale. Specifically, fibrosis scores correlated well with the LENT/SOMA scoring system (Spearman's rho 0.78, $p = 0.01$).

Brachial plexopathy is a potential toxicity associated with nodal irradiation. This side effect can significantly impair arm/shoulder function and worsen quality of life due to pain and paresthesia. Early trials of hypofractionated nodal irradiation conducted in Australia and Sweden in the 1960s revealed a 73% and 63% rate of neuropathy, respectively. However, the Australian regimen consisted of 63 Gy delivered in 12 fractions while the Swedish trial used 44 Gy in 11 fractions. Decades of experience have improved our understanding of the relationships between the volume of a critical structure treated, dose, fractionation and subsequent brachial plexus injury. We will also report this adverse effect using the LENT/SOMA scoring system.

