4.4 Blood Collection For Genomic Studies

The purpose of this portion of the study will be to collect blood from each subject accrued to the study and willing to donate a specimen of blood for research, to study the – 509C□T and +869T□C TGF- β 1 polymorphisms that have been reported to be correlated with the development of fibrosis following radiotherapy for treatment of breast cancer. [21]

For the purpose of this trial blood will be collected to enable genomic analysis for this polymorphism to explore association with the incidence of grade 3 and 4 late complications at 3 years follow up. Results of the blood test will be de-identified and will not be part of the patient's care. It will not be included in the medical record, but it will be maintained at the research office of the Department of Radiation Oncology at WCMC. When the study information is disclosed outside of WCMC as part of the research, the information that can identify the patient will be removed and the patient's records will be assigned a unique number. WCMC will not disclose the code key, except as required by law.

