16.3 Accrual estimates

Two distinct cohorts will be tested in this study. Based on the algorithm presented in study design (Page 9) some patients will need post-operative radiation to the breast/chest wall alone

(cohort 1) or to the breast and level III /SCV nodes (cohort 2). Since the fields of accelerated radiation are different the 2 cohorts will be accrued separately and analyzed separately.

Estimated number of eligible patients for the trial is 2-4/month. Therefore, we estimate that the required 74 patients (37 per cohort) will be recruited within 24-36 months.

With 37 patients, we can detect a difference of 18% from a baseline rate of 25% (grade II-III acute dermatitis) with a 2-sided $\alpha = 0.05$ and power of 80% using an exact binomial test. If we observe 15 or more events among these 37 patients, the null hypothesis that the rate is 25% will be rejected. Calculations from PASS 2008, NCSS.

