16.6 Statistical Analysis

16.6.1 Primary Endpoint

The primary endpoint is the occurrence of grade II or greater dermatitis within 60 days of the end of the treatment. The proportion of patients who experience this grade II or greater dermatitis will be estimated with exact 95% confidence intervals.

Patient demographic and disease characteristics at registration will be summarized using frequency distributions for qualitative data and summary statistics (means, medians, standard deviations, etc.) and graphical displays (e.g., Boxplots). Treatment data will be summarized similarly. Descriptive analyses will report the primary endpoint in subgroups defined by radiation regimen and other characteristics.

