16.6.2 Secondary Endpoints

See primary endpoint.

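### The toxicity denominator includes registered patients who were never irradiated, and late toxicity is a simple proportion with no fixed analysis time and no allowance for loss to follow-up

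*Combined protocol and SAP*

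**What the plan says.** All references are to the combined protocol and SAP.

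- **Population.** Section 16.2 defines one set: "All registered patients will be included in these analyses (intent to treat"). No treated, safety or evaluable set is defined.
- **Registration.** Under 6.2 a patient is registered once eligibility is confirmed and consent documented; starting radiotherapy is not required. Section 6.3 states that the trial is not randomised.
- **Primary analysis.** Section 16.6.1 counts dermatitis of grade II or worse up to 60 days from the end of treatment: "The proportion of patients who experience this grade II or greater dermatitis will be estimated with exact 95% confidence intervals". It also plans a treatment summary, and "Descriptive analyses will report the primary endpoint in subgroups defined by radiation regimen and other characteristics".
- **Decision rule.** Section 16.3: "If we observe 15 or more events among these 37 patients, the null hypothesis that the rate is 25% will be rejected".
- **Late toxicity.** Section 16.1.2 lists "Late toxicity 60 days post treatment including brachial plexopathy, fibrosis and telangiectasia; the proportion of patients with grades 2 or higher toxicity". The whole analysis text for secondary endpoints, in 16.6.2, is "See primary endpoint".
- **Late schedule.** Sections 7.3 and 13 set a visit at day 45-60 and then yearly visits for five years, with LENT/SOMA scoring. Section 4.4 names one late time point, for the genomic question only: to "explore association with the incidence of grade 3 and 4 late complications at 3 years follow up".
- **Censoring.** Section 16.6.3 plans Kaplan-Meier curves for recurrence-free and overall survival, not for late toxicity.

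**The concern.** In a randomised comparison, keeping everyone allocated protects the comparison. Here there is none to protect. A patient who never receives the regimen says nothing about its skin toxicity, yet she counts in the denominator. She also has no end of treatment, so the primary endpoint cannot be evaluated for her as written. Sections 16.2 and 16.6.1 can both be applied to her only with a further rule, and none is given. That rule could then be chosen after the data are seen, in a trial whose conclusion turns on an event count.

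The late endpoint has a related weakness. Patients followed for one year and for five years enter the same proportion with equal weight. If a patient lost early is treated as free of late toxicity, the reported rate falls below the true cumulative risk.

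**Working it through.** **Inputs.** From 16.3: 37 patients per cohort, null rate 25%, alternative 25% + 18% = 43%, rejection at 15 or more events. From 4.2: fibrosis is "another important late effect of radiotherapy with a commonly reported incidence of 5-15" percent, with no time horizon given. The documents give no non-start rate and no loss rate, so both are assumed below. The acute figures also assume exactly 37 registered per cohort; the Protocol Summary gives an accrual ceiling of 100 without saying what it is for.

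**The plan's own rule.** With n = 37 and a true 25%, P(X ≥ 15) = 0.0272 and P(X ≤ 3) = 0.0089. The minimum-likelihood two-sided exact p-value for 15/37 is their sum, 0.036, so the cut-off of 15 fits that convention. At a true 43%, P(X ≥ 15) = 67.8%. This is not the stated 80%, but that is a separate matter and nothing here depends on it.

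**Acute, m non-starters counted as event-free.** The rate reads p × (37 − m)/37, and the chance of rejection is P(X ≥ 15) with X ~ Bin(37 − m, p).

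| m | true 43% reads | true 25% reads | P(≥15) at 43% |
|---|---|---|---|
| 0 | 43.0% | 25.0% | 67.8% |
| 1 | 41.8% | 24.3% | 62.6% |
| 2 | 40.7% | 23.6% | 57.1% |
| 3 | 39.5% | 23.0% | 51.3% |

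**Acute, the opposite rule.** With m = 3 counted as events, a true 25% reads (0.25 × 34 + 3)/37 = 31.1%. P(15 or more) becomes P(X ≥ 12), X ~ Bin(34, 0.25), which is 11.9%. Under the event-free rule it is 1.2%, and with no non-starters 2.7%.

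**Does a treated set recover power?** That depends on the test convention.

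| Treated | Minimum-likelihood cut-off (p) | Power at 43% | Clopper-Pearson lower limit for 14 events |
|---|---|---|---|
| 36 | 15 (0.032) | 62.6% | 23.1% |
| 35 | 14 (0.0499) | 69.9% | 23.9% |
| 34 | 14 (0.045) | 64.8% | 24.65% |

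Judged by an exact (Clopper-Pearson) 95% interval, as 16.6.1 plans, 14 events do not exclude 25% at any of these sizes. The cut-off stays at 15 and power is 62.6%, 57.1% and 51.3%, the same as under the plan's fixed rule of 15. The plan's own 15/37 has a lower limit of 24.75%, so its cut-off and its interval already disagree at the margin.

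**Can the denominator change the conclusion?** It can in a particular case. Suppose 4 of 37 are not treated and 14 events occur. Over 37, p = 0.086. Over 33, p = 0.027 with exact interval 25.5% to 60.8%.

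**Late toxicity.** Take 15% as the 5-year risk, with constant hazards, loss independent of toxicity, no deaths, and lost patients counted as event-free. Then λ = −ln(0.85)/5 = 0.0325, ℓ = −ln(0.95) = 0.0513 or −ln(0.90) = 0.1054, and the crude proportion is λ/(λ+ℓ) × [1 − exp(−5(λ+ℓ))].

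- 5% yearly loss: 0.388 × 0.342 = 13.3%, or 4.9 events in 37 against 5.6 (37 × 0.15).
- 10% yearly loss: 0.236 × 0.498 = 11.7%, or 4.3 events, a gap of about 1.2.
- At the low end, a true 5% reads 4.4% or 3.9%.

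The exact 95% interval for 5/37 is 4.5% to 28.8%, far wider than these gaps.

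**The case against.** The case for leaving the text alone has substance.

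- **Few non-starters are likely.** Surgery must be complete before accrual (6.1, 8.0) and patients are already referred for radiation. The treatment summary and regimen subgroups in 16.6.1 may also show any non-starters. This stands as a reason to expect a small effect, but it does not define the primary denominator.
- **Direction.** A reader might infer that the plan biases toxicity downward. The text does not support that: 16.2 says who is included, not how an unobserved patient is scored, and the opposite rule raises the rate.
- **Off-protocol irradiation.** A reader might take 7.4 as evidence that registered patients cross to the six-week course. That section describes an alternative offered at accrual and says nothing about later crossover.
- **Missing acute assessments.** Toxicity is scored weekly and at day 45-60 (section 13), so a treated patient with no acute assessment at all is unlikely. The lack of a rule for that case is missing detail and is not pressed here.
- **Late timing.** To say that no late evaluation time exists would go too far. Yearly visits are scheduled, and the 60 days in 16.1.2 can be read as the boundary between acute and late. What is missing is the time point at which the grade 2 or higher proportion is analysed.

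**Conclusion.** The point holds as a minor one. The plan keeps never-irradiated patients in a single-arm toxicity denominator for an endpoint that is undefined for them, and carries a simple proportion over to an outcome followed for five years.

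With an assumed 3 non-starters in 37, a true 25% reads between 23.0% and 31.1% depending on an unstated rule. The real number is unknown and the effect is probably small. The late understatement is at most about 1.2 events in 37 under the assumed loss rates, and it also rests on reading 15% as a 5-year risk and on lost patients counting as event-free.

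Two stronger conclusions are not supported. With one to three non-starters, a treated set does not reliably restore power: the gain over the fixed rule of 15 appears under the minimum-likelihood test and disappears under the planned interval. And no late-toxicity decision is put at risk, because that rate carries no threshold or test. The gain from a change is an interpretable denominator and a rule fixed in advance.

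**What to change.** **Section 16.2.** Define the toxicity set as registered patients who receive at least one protocol fraction. Report, by cohort, the number registered but not treated. Restate the exact cut-off for the number actually treated, and name the two-sided convention used, so that the test and the reported interval can be reconciled.

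**Section 16.6.2.** For late toxicity, replace the cross-reference with stated yearly time points. Report grade 2 or higher fibrosis, telangiectasia and brachial plexopathy as cumulative incidence with 95% confidence intervals, censoring at the last LENT/SOMA assessment and treating death as a competing event. Give the number assessed at each visit. With roughly 2 to 6 events expected per cohort on the 5-15% range, the time points and the numbers assessed matter most.

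**Cost.** SAP wording and slightly more analysis of data already scheduled in section 13, with no added visits and no change to treatment. The denominator may be slightly smaller and the reported toxicity slightly higher.

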16.3 Accrual estimates

Two distinct cohorts will be tested in this study. Based on the algorithm presented in study design (Page 9) some patients will need post-operative radiation to the breast/chest wall alone

(cohort 1) or to the breast and level III /SCV nodes (cohort 2). Since the fields of accelerated radiation are different the 2 cohorts will be accrued separately and analyzed separately.

Estimated number of eligible patients for the trial is 2-4/month. Therefore, we estimate that the required 74 patients (37 per cohort) will be recruited within 24-36 months.

With 37 patients, we can detect a difference of 18% from a baseline rate of 25% (grade II-III acute dermatitis) with a 2-sided $\alpha = 0.05$ and power of 80% using an exact binomial test. If we observe 15 or more events among these 37 patients, the null hypothesis that the rate is 25% will be rejected. Calculations from PASS 2008, NCSS.

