Adding network sites	Adding NYP-BMH, NYP-Q as addition sites for patient enrollments	Adding sites

Summary of changes: Version 4.0 dated 06.30.2020

Adding to the eligibility criteria:

1. To include patients who because of COVID had undergone up to 3 months neoadjuvant hormonal therapy before surgery for clinical T1/T2 BC
2. Video visits will be included as part of patient follow up.
3. Removing [name] from the study as she is no longer working in WCM Radiation Oncology.

Rationale for the changes: NCI wants to assure most patients who had modifications during COVID are still eligible to clinical trials.

Summary of changes: Version 3.0 dated 10.11.2019

1. Adding [name] to the study.
2. Formatting the protocol as the index is not correctly formatted.
3. Making the protocol version date consistent on the header text.

No Changes to the informed consent.

Summary of changes: Version 2.1 dated 05.04.2018

1. Making the investigators' list consistent with eIRB.
2. Changing study coordinator to [name]

Exclusion Criteria Section 5.2:

1. Adding: Patients with more than 5 nodes involved at axillary dissection will be excluded from this study since they will be eligible to receive radiotherapy to level I and II axilla.

This was already written in the body of the protocol (section 9.0 Radiotherapy) but was not included in the exclusion Criteria section 5.2.

Summary of Changes: Version 2.0 Dated 10.09.2017.

1. Title Change : Accelerated Radiation Therapy (Art) To The Breast And Nodal Stations After Neo-Adjuvant **Systemic Therapy** And Surgery: A Feasibility Study
 - Rationale for title change : To include neoadjuvant hormone therapy
2. Cohort 2 to include: If clinically indicated, internal mammary nodes will also be treated and a supine set up will be used
 - Rationale - To follow the most recent NCCN indications to irradiate internal mammary nodes for inner quadrants and central cancers, particularly if axillary nodes are also involved

PROTOCOL SUMMARY

Full Title:	ACCELERATED RADIATION THERAPY (ART) TO THE BREAST AND NODAL STATIONS AFTER NEO-ADJUVANT SYSTEMIC THERAPY AND SURGERY: A FEASIBILITY STUDY
Short Title:	ART Protocol
Clinical Phase:	Phase I-II
Principal Investigator:	[name]. [name]
Sample Size:	N= 74 (37 per Arm)
Accrual Ceiling:	100
Rate of subject accrual:	Approximately 3 subjects per month or 36 patients per year

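### The stated 80% power is wrong: with 37 patients per cohort and rejection at 15 or more events, exact power at 43% is 68%, and 80% is reached only at a true rate of about 46%.

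*Combined protocol and SAP*

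**What the plan says.** Section 16.3 (Accrual estimates) sets 37 patients per cohort, 74 in total, and says that "the 2 cohorts will be accrued separately and analyzed separately". The claim for each cohort is: "With 37 patients, we can detect a difference of 18% from a baseline rate of 25% (grade II-III acute dermatitis"). The error level is two-sided 0.05, and the section claims "power of 80% using an exact binomial test". It then gives the decision rule: "If we observe 15 or more events among these 37 patients, the null hypothesis that the rate is 25% will be rejected". The calculation is attributed to PASS 2008.

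The 25% null is also the limit in the primary objective of the Protocol Summary, which is grade 2-3 dermatitis below 25% in each cohort. Section 16.2 analyses all registered patients, and section 16.5 plans no interim analysis. For reporting, section 16.6.1 says: "The proportion of patients who experience this grade II or greater dermatitis will be estimated with exact 95% confidence intervals". It does not name the interval method.

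**The concern.** Sample size, null rate, alternative, alpha, test and rejection count are all printed, so the power follows from a single binomial tail probability. That probability is well below 80%.

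The rule rejects when toxicity is high, so the favourable outcome is a non-rejection, at 14 or fewer events. Power is what tells a reader how much a non-rejection means. As written, section 16.3 invites the reading that 14 or fewer events gives 80% assurance against a 43% rate of grade II-III dermatitis. If the true figure is 68%, the plan overstates in each cohort its ability to detect excess acute skin toxicity.

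**Working it through.** **Inputs, all from section 16.3.** n = 37 per cohort; null rate p0 = 0.25; difference 0.18, so p1 = 0.25 + 0.18 = 0.43; two-sided alpha 0.05; exact binomial test; reject at X ≥ 15; stated power 0.80. There is no interim analysis (16.5) and all registered patients are analysed (16.2), so nothing else enters.

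**Formula.** P(X ≥ r | n, p) = Σ C(n, k) p^k (1 − p)^(n − k), summed over k = r, …, n.

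**Attempt to reproduce 80%.**

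| Cut-off | P(X ≥ cut-off) at 25% | P(X ≥ cut-off) at 43% |
|---|---|---|
| 14 | 0.0577 | 0.787 |
| **15 (as printed)** | **0.0272** | **0.678** |
| 16 | 0.0117 | 0.551 |

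At the printed cut-off the power is 0.678, so the type II error is 1 − 0.678 = 0.322 against the implied 0.20.

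**Is the cut-off of 15 consistent with two-sided 0.05?** This depends on how the two-sided exact test is built, which 16.3 does not say.

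- *Minimum-likelihood test* (add up all outcomes no more probable under 25% than the one observed). At 15 events these are X ≤ 3 and X ≥ 15: p = 0.0089 + 0.0272 = 0.036, which rejects. At 14 events they are X ≤ 4 and X ≥ 14: p = 0.0284 + 0.0577 = 0.086, which does not. The upper cut-off is therefore 15. The lower region X ≤ 3 adds only about 0.000003 to power at 43%.
- *Equal tails* (0.025 each side). At 15 events the upper tail is 0.0272, above 0.025, and the doubled p-value is 0.054. The cut-off would be 16, with power 0.551.

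Of the two, 68% is the reading kinder to the plan.

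**Where 80% is reached with cut-off 15.** P(X ≥ 15 | 37, p) is 0.720 at p = 0.44, 0.760 at 0.45 and 0.797 at 0.46. Solving for 0.80 gives p = 0.461, a difference of 0.461 − 0.25 = 0.211.

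**Other routes to 80%.**

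- Two-sided normal approximation: Φ[(0.18√37 − 1.96√(0.25 × 0.75)) / √(0.43 × 0.57)] = 0.691, or 0.630 with continuity correction. Arcsine: 0.645.
- One-sided 0.05 normal approximation (1.645 in place of 1.96): 0.780, or 0.812 with the null variance only. This is neither exact nor two-sided.
- A fall of 18 points, to 7%: exact power 0.742 (X ≤ 3) or 0.886 (X ≤ 4, whose two-sided p is 0.056). The printed rule points upward in any case.

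No route that keeps the stated test, alpha and cut-off gives 80%. The documents do not show where the figure came from.

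**Size that would give 80% at 43%.** Under the minimum-likelihood test the first is n = 50 per cohort (cut-off 19, power 0.804, two-sided size 0.048). Every n from 37 to 49 falls short; the best is 0.787, at n = 47.

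**Side check on the interval in 16.6.1.** At 15/37 the Clopper-Pearson 95% interval is 24.75% to 57.9%, which just includes the 25% that the rule rejects. Inverting the minimum-likelihood test gives 25.4% to 56.8%, which excludes it. The two disagree about 25% only at exactly 15 events.

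**The case against.** The arithmetic is not in dispute; the objections concern certainty and weight.

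- *The cut-off might be the error, not the power.* Section 16.3 does not name the two-sided construction, and with equal tails 15 events would not reject. This stands as a caveat: 68% belongs to the printed rule, which is a valid two-sided 0.05 test only under the minimum-likelihood definition. It does not rescue 80%, because the equal-tailed test has lower power (55%).
- *The consequence is limited.* Section 16.4 is marked not applicable, there is no interim analysis, and the written primary analysis is an estimate with a confidence interval, which is valid whatever power was claimed. This is correct and confines the harm to justification and interpretation. It does not make a wrong power figure for the primary endpoint acceptable.
- *The interval wording is a matter of preference.* Largely so. Keeping Clopper-Pearson and noting the disagreement at exactly 15 events would also be defensible.
- *Fifty per cohort is fragile.* This stands. Exact power is saw-toothed: it falls to 0.753 at n = 51 and 0.788 at n = 52, so one extra registered patient in a cohort would break the claim. With equal tails the first adequate size is 55 per cohort, or 110 in total, above the accrual ceiling of 100.

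**Conclusion.** The power statement in section 16.3 is wrong as written. For the printed rule, power at 43% is 67.8%, about 12 points below the stated 80%, and the type II error is 32.2% instead of 20%. With 37 patients and a cut-off of 15, 80% power applies to a true rate of 46.1%, a rise of about 21 points. The upper-tail error at 25% is 0.027 and the two-sided size is 0.036.

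The power figure rests only on inputs printed in 16.3. The acceptability of 15 as the cut-off rests further on the minimum-likelihood form of the two-sided exact test. The error affects both cohorts. Fourteen or fewer events cannot be presented as 80% assurance against a 43% rate.

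**What to change.** Keep 37 per cohort and the cut-off of 15, and replace the power sentence in section 16.3 with:

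> With 37 patients per cohort and rejection of a 25% rate at 15 or more events (two-sided minimum-likelihood exact binomial test, alpha 0.05), power is 68% at a true rate of 43% and 80% at about 46%; the exact upper-tail error at 25% is 0.027.

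The cost is one sentence and a less favourable figure; there are no extra patients.

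A secondary, optional change is to say in 16.6.1 that the exact 95% interval is obtained by inverting the same minimum-likelihood test, so that interval and rule agree at 15/37. That is one phrase.

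Only if 80% power at 43% is a firm requirement would the size need to change. Under the minimum-likelihood test that means exactly 50 per cohort with cut-off 19, or 100 in total, which uses the whole accrual ceiling. It costs 100 − 74 = 26 more patients: about 26/3 ≈ 9 months at the Protocol Summary's 3 per month, or 6.5 to 13 months at the 2-4 per month of section 16.3. This assumes that both cohorts fill at a similar pace; otherwise the slower one sets the duration.
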